1.2 Schema

1.3 Schedule of Activities – Group 1

It is anticipated that 12 clinicians will be included in the study, and up to 51 patients who are cared for by those clinicians. Eight to ten patients will enter the study cohort each week for 6 weeks.

For informational purposes, whether the research team performs the activity, or the anticoagulation clinic staff performs the activity is indicated in bold. Failure of the anticoagulation clinic staff to follow the clinical protocols for delivery of the patient and clinician level QI strategies will not be considered study deviations.

Schedule of Patient-Targeted Activities

Activity	Screening and randomization	Week 1	Week 2-4	Week 5-8	Week 9-12	Week 15-17	Week 13-28
Eligibility determination by chart review (research team)	X						
Randomization of patient to QI strategy (research team)	X						
Delivery of education and activation guide for patients randomized to receive it (anticoagulation staff)		X					
Possible outreach to the patient by their clinical care team and/or anticoagulation clinic staff as per usual clinical care (no research team activity)		X	X	X			
Administration of patient assessment #1 by phone, with waiver of informed consent (research team)				X			
Verbal informed consent followed by patient assessment #2 (research team)				X			
Administration of patient assessment #3 by phone, with verbal informed consent (research team)							X
Chart review to ascertain exploratory outcomes (research team)	X	X	X	X	X	X	X

Activity	Screening and randomization	Week 1	Week 2-4	Week 5-8	Week 9-12	Week 15-17	Week 13-28
Chart review to determine appropriateness of initial and subsequent use of antiplatelet therapy (research team)							X

Schedule of Clinician-Targeted Activities

Activity	Screening, selection, and randomization	Week 1-5	Week 6-10
Eligibility determination (research team)	X		
Randomized selection of 12 clinicians to be included (research team)	X		
Randomization of selected clinicians to either clinician notification arm or clinician notification + nurse facilitation arm (research team)	X		
Delivery of clinician-facing QI strategies, synchronized with patient-level strategies (anticoagulation clinic staff)		X	
Additional outreach, communication, or facilitation steps as per anticoagulation clinic protocol for clinician notification and clinician notification + information relay strategies (anticoagulation clinic staff)		X	

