Verbal informed consent and semi-structured interviews with clinicians (research team) . This may occur as soon as week 5 if the clinician has already responded to messages for all of their patients involved in the trial.		X	X

Schedule of Anticoagulation Clinic Staff-Targeted Activities

Activity	Week 1-5	Week 6-8	Week 9-16
Anticoagulation clinic staff receive weekly list of up to 10 patients starting trial each week, and the name of the target clinicians (research team)	X		
Anticoagulation staff initiate clinician and patient facing QI strategies synchronously (anticoagulation clinic staff)	X		
Additional outreach, communication, or facilitation steps as per anticoagulation clinic protocol for clinician notification and clinician notification + nurse facilitation strategies (anticoagulation clinic staff)	X	X	
Verbal informed consent and semi-structured interviews with anticoagulation staff (research team)			X

1.4 Schedule of Activities – Group 2

A convenience sample of 8 primary care clinicians will be selected. Additionally, all eligible patients for whom the primary care clinician is the responsible provider on record for the anticoagulation clinic will be included in group 2. We anticipate that each included primary care clinician will have 1-2 eligible patient included in group 2, for a total of 8-16 patient participants.

For informational purposes, whether the research team performs the activity, or the anticoagulation clinic staff performs the activity is indicated in bold. Failure of the anticoagulation clinic staff to follow the clinical protocols for delivery of the patient and clinician level QI strategies will not be considered study deviations.

Schedule of Patient-Targeted Activities

Activity	Screening and randomization	Week 1	Week 2-4	Week 5-8	Week 9-12
Eligibility determination by chart review (research team)	X				

Activity	Screening and randomization	Week 1	Week 2-4	Week 5-8	Week 9-12
Randomization of patient to QI strategy (research team)	X				
Delivery of education and activation guide for patients randomized to receive it (anticoagulation staff)		X			
Possible outreach to the patient by their clinical care team and/or anticoagulation clinic staff as per usual clinical care (no research team activity)		X	X	X	
Chart review to ascertain exploratory outcomes (research team)			X	X	X

Schedule of Clinician-Targeted Activities

Activity	Screening, selection, and randomization	Week 1	Week 2-6
Eligibility determination (research team)	X		

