4 OBJECTIVES AND ENDPOINTS

4.1 Objectives and Endpoints (Group 1)

OBJECTIVES	ENDPOINTS
Primary	
To explore the feasibility of patient participation in a one-time assessment of medication use following delivery of the QI strategies.	Proportion of patient participants who are able to be contacted by phone and are willing to participate in and fully complete patient assessment #1, related mainly to medication use (week 5 interview).
Secondary	
To explore the feasibility of delivering QI strategy components as intended.	Proportion of participants who received all implementation components to which they were randomized in the appropriate time frame.
Exploratory	
To explore additional aspects of the feasibility of recruitment.	Proportion of randomized patients able to be reached by phone after three attempts for patient assessment #1 at week 5. Average number of phone call attempts to reach each patient for patient assessment #1 at week 5. The number of anticoagulation clinic patients who meet eligibility criteria for the AEGIS trial on the first day of the pilot study according to the EHR workbench report.
To explore changes in the proportion of eligible patients during the study duration.	The proportion of all patients in the anticoagulation clinic who meet eligibility criteria for the study, regardless of whether they are included, who discontinued warfarin or were otherwise closed to the anticoagulation service during the study period. The proportion of patients who were randomized who discontinued warfarin or were closed to the anticoagulation clinic service during the participants' study duration.

OBJECTIVES	ENDPOINTS
To explore the accuracy of the electronic health record's medication list for ascertaining inclusion criteria	
The proportion of randomized patients who, retrospectively, report that they had been using antiplatelet therapy at baseline during patient assessment #1 at week 5.
 
The proportion of randomized patients who, retrospectively, report that they had been using PPI at baseline during patient assessment #1 at week 5.
 
The proportion of randomized patients who met inclusion criteria based on retrospective medication use in patient assessment #1 at week 5.

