6.4 Patient and Clinician Selection

6.4.1 Group 1

At random, we will choose 12 Michigan Medicine clinicians who either serve as the cardiologist for (n=6), or the (non-cardiologist) clinician of record (n=6) for patients in the anticoagulation clinic. For each of these clinicians, we will include all of their patients who meet eligibility criteria based on chart review. We anticipate the number of included patients will be 40-51. Eligibility will be determined based on information in the electronic health record. All participants will be screened for eligibility in the week prior to study entry.

6.4.2 Group 2

We will select a convenience sample of 8 Michigan Medicine clinicians who are the clinician of record for patients in the anticoagulation clinic and specialize in primary care from a convenience sample. For each of these clinicians, we will include all of their patients who meet eligibility criteria based on chart review. Eligibility will be determined based on information in the electronic health record. All participants will be screened for eligibility in the week prior to study entry.

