8.3 Lost to Follow-Up

8.3.1 Group 1

If a patient is unable to be reached for assessment #1, #2, or #3, the data for the variables associated with that assessment will be coded as missing. If a patient is unable to be reached for assessment #1, no attempt will be made to reach them for assessment #2 or assessment #3. Even if patients are unable to be reached for assessment #1, #2, or #3, chart review will still be performed for that patient to evaluate the exploratory outcomes.

8.3.2 Group 2

Not applicable as no patient assessments will be conducted with group 2 participants. Chart review will be performed for patients in group 2 between study initiation and week 6.

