One-time semi-structured qualitative interviews will be conducted with up to 12 clinicians who received communications from the anticoagulation clinic as part of this project. The interviews will be conducted 5-10 weeks after the last patient in the clinician-cluster entered into the study. Clinicians will be sent an invite to participate in an hour-long phone or zoom interview at their institutional email address by a research assistant. Clinicians will be offered a \$100 gift card as an incentive for participation. Qualitative interviews with clinicians will focus on clinicians'

perceptions of the acceptability of the QI strategies and on feasibility of responding to the messages and initiating medication changes for GI bleeding risk reduction. Written informed consent will be obtained using SignNow software.

9.2.2 Patients:

- **Patient Assessment #1 (Week 5):** A research assistant will contact all patient participants by phone at week 5 to administer patient assessment #1, expected to take no more than 10 minutes to complete, with the patient's permission. This questionnaire will ask patients about the medications they used ~30 days prior and the medications that they currently use. All patients will be asked whether they have had any changes in their medications in the past month, or if they have had a discussion with a healthcare provider about any medication changes or their risk of bleeding. Patients who were randomized to receive the activation tool will additionally be asked whether they recall receiving any educational materials about bleeding risk from the anticoagulation clinic to assess the feasibility of delivering patient education and activation materials. If the patient self-reports any use or non-use of medications that contradicts the information in their MiChart medication list, the research assistant will send a MiChart message to the patient's anticoagulation clinic nurse so that the nurse can reconcile the chart. No remuneration will be offered with this patient contact. We request a waiver of informed consent for patient contact #1. **Data on the ability to reach patients for this evaluation will be used to assess the pilot trial's primary outcome. Up to three contact attempts over a period of 2 weeks will be made to reach each patient for assessment #1.**

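### The baseline question in assessment #1 is tied to the call date rather than study entry, so for patients reached late it can point to a date after the strategies were delivered

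*Combined protocol and SAP*

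**What the plan says.** Eligibility is read from the EHR close to entry. Section 6.4.1 states: "All participants will be screened for eligibility in the week prior to study entry". In the Group 1 schedule (section 1.3) the activation guide goes out in the patient's week 1. The staff table there links the clinician messages to it: "Anticoagulation staff initiate clinician and patient facing QI strategies synchronously".

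On the call itself, section 9.2.2 says: "A research assistant will contact all patient participants by phone at week 5 to administer patient assessment #1". It then sets the contact window: "Up to three contact attempts over a period of 2 weeks will be made to reach each patient for assessment #1". The recall question is defined relative to the call: "This questionnaire will ask patients about the medications they used ~30 days prior and the medications that they currently use". Patients are also asked about medication changes over the past month.

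Section 4.1 uses the answers for three exploratory endpoints on how well the EHR medication list establishes inclusion. The first is: "The proportion of randomized patients who, retrospectively, report that they had been using antiplatelet therapy at baseline". The second is the parallel proportion for PPI use, and the third is the proportion who met the inclusion criteria on recalled use. Section 12.1.1.2 confirms that the call is meant to check the EHR both at baseline and at the time of the call.

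For patients who cannot be reached, section 8.3.1 says that "the data for the variables associated with that assessment will be coded as missing".

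**The concern.** The endpoints need medication use at entry. The question asks for use about 30 days before the call. The two coincide only if the call comes about 30 days after entry, and the contact window allows it to come later.

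Where they differ, the error runs one way. A patient who stops the antiplatelet before the recall date appears not to have met the inclusion criterion in section 6.2.1. A patient who starts a PPI before that date appears to have met the exclusion in section 6.3.1. In both cases the EHR was right at screening and is scored as wrong. These are the changes the strategies are meant to produce, so the misreading falls on early responders.

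At stake is one planning input for the future clinic-wide trial: how far the EHR medication list can be trusted to select patients.

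**Working it through.** **Inputs.** Day 1 is study entry, week w covers days 7w-6 to 7w, and day 0 is the day before entry. Delivery is in week 1, days 1-7 (section 1.3). Calls start in week 5, days 29-35, with attempts over 2 weeks and recall of about 30 days (section 9.2.2).

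**The plan's own figure.** A week-5 call comes 29 - 1 = 28 to 35 - 1 = 34 days after entry. About 30 days is therefore a fair proxy for entry when the call is made in week 5.

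**Recall date = call day - 30.**

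| Call day | When it arises | Recall date |
|---|---|---|
| 29 | first day of week 5 | day -1 |
| 35 | last day of week 5 | day 5 |
| 38 | early week 6 | day 8 |
| 42 | 2 weeks counted from the start of week 5 | day 12 |
| 49 | 2 weeks counted from a first attempt at the end of week 5 | day 19 |

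Day 38 is the first call day whose recall date lies wholly after the delivery week (38 - 30 = 8 > 7). That leaves 5 of 14 possible call days if the window closes on day 42 (days 38-42 out of 29-42), and 12 of 21 if it closes on day 49 (days 38-49 out of 29-49). These are counts of calendar days, not of calls.

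**Do other parts of the plan repair this?**

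- The question on changes in the past month moves with the call. For a call on day 42 it reaches back to about day 12, so a change on day 5 falls outside it as well.
- Chart review (section 9.6.1) records documented medication changes, but no rule uses them to correct the recalled baseline.
- Section 3.1 recognises that patients may stop aspirin or start a PPI themselves, over the counter. Such changes may never be charted.

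**Size.** The documents give neither the share of respondents reached late nor the share of those who changed before the recall date. I assume 20-50% and 5-20%.

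- Share of respondents misread: 0.20 x 0.05 = 1% to 0.50 x 0.20 = 10%.
- Respondents at the 80% rate used in section 11.1.1: 0.80 x 40 = 32, or 0.80 x 51 = 41 (rounded).
- Patients misread: 0.3 to 3.2 of 32, or 0.4 to 4.1 of 41.

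**After re-anchoring.** If the question names the entry date, the drift is zero for every call day. The recall interval then varies from 29 - 1 = 28 to 49 - 1 = 48 days.

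**The case against.** The best defence is that the stated interval is an explicit approximation that fits the planned week-5 call, and that sections 4.1 and 12.1.1.2 make it clear that baseline is what is meant. The questionnaire itself is not in the documents and may give the patient a date. Patients may also be unable to separate a month ago from six weeks ago. An error needs a late call, an early change and fairly precise recall, all in the same patient. Charted early changes could be recognised on review.

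Much of this stands: it limits the size and confines the problem to patients reached late. It does not remove the gap, because nothing in the protocol ties the question to entry and the only described form of it moves with the call.

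Three stronger readings are tempting, and the documents support none of them:

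- **That most calls are affected.** No distribution of call dates is given, and a call made in week 5 as planned points to a date before or within the delivery week.
- **That the week-5 effectiveness endpoint loses real changes.** Section 4.1 defines it as PPI initiation or antiplatelet discontinuation by patient interview. Current use is asked directly, and every randomized patient was charted at entry as on an antiplatelet without a PPI. The endpoint is affected only if change is judged against the recalled baseline, which no section says.
- **That naming randomized patients as the denominator pulls the accuracy figures down.** At 80% completion and an illustrative 90% accuracy, 0.80 x 0.90 = 72%, but only if missing answers count as failures. Section 8.3.1 codes them as missing. For the PPI endpoint, counting missing as non-use would make the EHR look better, not worse. What remains is wording to clarify.

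**Conclusion.** The point holds for patients reached from about day 38 on. For them the protocol's recall date falls after the delivery week, and a prompt medication change can be scored as an EHR eligibility error. The three exploratory baseline-accuracy endpoints in section 4.1 are exposed. The primary endpoint (completing assessment #1, section 9.4.1) and the secondary endpoint (delivery by chart review, section 9.5.1) are not.

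The effect is probably small: about 0-4 patients among 32-41 respondents. That range rests on the assumed shares above, and its top requires half of respondents to be reached late and a fifth of those to have changed already. The timing assumes that day 1 is entry and that delivery is completed in week 1. The upper limit of day 49 further assumes that the 2 weeks run from a first attempt at the end of week 5; otherwise the limit is about day 42. The point is worth acting on because the error is directional, the sample is small and the remedy is nearly free.

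**What to change.** In section 9.2.2 and the assessment #1 script:

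- Ask what the patient was taking just before their own study-entry date, with the caller stating the date.
- Ask about changes since that date instead of over the past month.
- Record the date of the call.

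In section 4.1, as a minor clarification, state that the three baseline-accuracy proportions are computed among patients who completed assessment #1.

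The cost is two changed script questions, one extra data field and one sentence on the denominator. Section 4.1 already provides for revising the interview guides during the pilot. The one drawback is that recall length would vary from about 28 to 48 days, so patients reached late must remember further back. With the call date recorded, that can be examined.

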To explore the accuracy of the electronic health record's medication list for ascertaining medication changes	
The accuracy, positive predictive value, and negative predictive value of the electronic health record for use of antiplatelet therapy, and for use of PPIs at the time of assessment #3.
 
The accuracy, positive predictive value, and negative predictive value of the electronic health record for "medication optimization" at the time of assessment #3. A patient will be considered to have had medication optimization if they are either no longer using combination antithrombotic therapy or are using a PPI.

To explore the feasibility of complete collection of study data	
The proportion of patients with complete data entry in RedCAP database at study completion
 
Average duration of interviews on medication use/adherence during patient assessment #3 at week 15-17.

To explore the feasibility of delivering the clinician-level QI strategies	
Proportion of patients whose clinician was sent the clinician-level strategy by the anticoagulation clinic staff in the prescribed time period per the clinic protocol. We will also separately calculate this endpoint for the two levels of the clinician QI strategy.

To explore the feasibility of delivering the patient activation tool	
The proportion of patients randomized to receive the activation guide who were sent the guide in the prescribed period of time, as determined by chart review.
 
The proportion of patients randomized to receive the guide who recalled receiving the guide during patient assessment #1 at week 5.
 
The proportion of patients randomized to receive the guide who recalled reviewing the guide in patient assessment #1 at week 5.

OBJECTIVES	ENDPOINTS

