6.6 Strategies for Recruitment and Retention

6.6.1 Group 1

This trial will be conducted as a pragmatic quality improvement initiative in partnership with the Michigan Medicine anticoagulation clinic service. As knowledge of their participation in this study prior to receipt of the QI implementation strategies could result in unintended reactivity, in which the participant changes their behavior in response to knowing they are being observed, and harm the integrity of the study, patient and clinician participants will not be actively recruited for this study prior to delivery of the implementation strategies and no strategies will be used for participant retention. However, to complete the assessments for the study to evaluate the feasibility and acceptability of the Qi strategies, we will contact patients by phone up to 3 times over the period of 2 weeks to administer a brief 5-10 minute phone assessment to assess the accuracy of the electronic health record and determine whether the patient received the implementation strategies. Patient phone numbers will be obtained from the electronic health record and a voicemail will be left for the patient if they are unable to be reached at any of the 3 contact attempts. The research team will also contact clinician and anticoagulation clinic staff participants at their institutional email address to invite them to participate in a one-time, hour long qualitative assessment to elicit feedback about their experience with the implementation strategies and feasibility of continuing the project. Clinician and staff email addresses will be obtained from Michigan Medicine departmental websites or the University directory.

6.6.2 Group 2

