 - At the end of this call, patients who self-report having had a discussion with their clinician and those who were randomized to receive the patient activation tool will be invited to take part in a second 60-minute phone research interview within the next 3 weeks(patient assessment #2). All patients who complete assessment #1 will additionally be invited to participate in another medication review call at week 15-17 to assess durability of medication changes (patient assessment #3).
- **Patient Assessment #2 (Week 5-8):** A research assistant will contact a subset of participants (as described above) to participate in an hour-long semi-structured qualitative phone or zoom interview for patient assessment #2. The interview will elicit patient perceptions about the patient activation tool and about any discussions the patient may have had with one of their clinicians about their risk of bleeding and/or ways to reduce that risk. Prior to the interview, patient's will be provided with an informed consent document approved by the IRB at the University of Michigan and given the chance to ask any questions they may have. Patient's will then be asked to provide verbal consent before the interview may begin. Patient's will be advised that participation is entirely voluntary and choosing not to participate will not affect the care they may receive at Michigan Medicine. They will also be instructed that they can decline to answer any questions or end the interview at any time shall they wish. As all interviews will be conducted over the phone or zoom, and do not deal with sensitive or stigmatized subjects, we request a waiver of documentation of written informed consent for patient

assessment #2. Patients will receive a \$20 gift card as remuneration for participating in this assessment. Patient remuneration will be sent through the University of Michigan treasurer's office human subjections incentives payment program gift card payment option.

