11.7 Exploratory Analyses

11.7.1 Group 1

Exploratory analyses will mainly consist of descriptive analyses using cross-tabulations, means, standard deviations and proportions. The accuracy, positive predictive value, and negative predictive value will be calculated for antiplatelet use, PPI use, and “medication optimization” at multiple time points, comparing the EHR medication list to self-report (reference standard).

11.7.2 Group 2

Exploratory analyses will mainly consist of descriptive analyses using cross-tabulations, means, standard deviations and proportions.

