12.1.1.2 Patient assessment #1 (Group 1 only)

Obtaining informed consent from patient and clinician participants prior to delivery of the implementation strategies could harm the integrity of the study by priming participants to respond to communications or notifications from the anticoagulation service or initiate a medication change for bleeding risk reduction.

Patients and clinicians will not be consented prior to receipt of any implementation strategies delivered as part of the quality improvement project in an attempt to reduce reactivity and the Hawthorne Effect and ensure integrity of the study. Additionally, we request a waiver of informed consent for assessment #1 with patients. Patient assessment 1 will consist of a one-time phone questionnaire anticipated to take 10 minutes or less to complete and will solely include questions that will allow the anticoagulation clinic to ensure that information in MiChart related to medications that influence bleeding risk are accurately documented in the patient's EHR both at baseline and at the time of the call and to assess whether the patient-facing

implementation strategy (activation tool) was received by the patient. Accurate patient medication information in MiChart and knowledge of whether the tool was received by the patient are necessary to correctly identify patients at high-risk for adverse events associated with warfarin use and ensure that patient education and activation materials can be delivered in a timely-fashion, and as such are in-line with quality improvement efforts.

As consenting patients and/or clinicians prior to their randomization or receipt of the implementation strategies may result in unintended reactivity or the Hawthorne Effect which could harm the integrity of the study and influence study results, the study team will seek a waiver of informed consent from the IRB at the University of Michigan for patient assessment #1.

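### Study-prompted chart corrections at week 5 precede the exploratory EHR-accuracy result at assessment #3, and a medication-list change alone can be scored as a clinician recommendation

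*Combined protocol and SAP*

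**What the plan says.** **The correction step.** Assessment #1 asks about medicines used about 30 days earlier and medicines used now. A contradiction with MiChart leads to a message to the patient's "anticoagulation clinic nurse so that the nurse can reconcile the chart" (section 9.2.2). Assessment #3 has the same provision. Section 12.1.1.2 makes correct charts a purpose of the first call, which is limited to "questions that will allow the anticoagulation clinic to ensure that information in MiChart related to medications that influence bleeding risk are accurately documented" and to checking receipt of the guide. Section 6.6.1 gives the same call a measurement purpose as well: "to assess the accuracy of the electronic health record and determine whether the patient received the implementation strategies".

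**Who reaches #3.** Section 9.2.2 states: "All patients who complete assessment #1 will additionally be invited to participate in another medication review call at week 15-17". Under section 8.3.1, a patient not reached for #1 is not tried for #3, but the chart is still reviewed.

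**The accuracy endpoints.** Section 4.1 lists, as exploratory, the accuracy, PPV and NPV "of the electronic health record for use of antiplatelet therapy, and for use of PPIs at the time of assessment #3", and the same measures for medication optimization. The stated objective is the accuracy of the record's "medication list for ascertaining medication changes". Section 11.7.1 plans these measures "at multiple time points, comparing the EHR medication list to self-report (reference standard" without naming the time points. A separate set of section 4.1 endpoints covers baseline use, such as patients who "report that they had been using antiplatelet therapy at baseline during patient assessment #1 at week 5".

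**The recommendation endpoint.** Section 4.1 counts a recommendation by one of the patient's clinicians to stop antiplatelet therapy or start a PPI. Either a clinical note or a medication-list change may serve as the indicator. The chart-review row in section 1.3 is marked in every window, from screening to week 28.

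**The concern.** Assessment #1 both measures and repairs the medication list. The accuracy result at #3 comes some 10 to 12 weeks later (section 12.1.1.4), and every patient in it has passed through the repair step. List errors arising from medication changes between baseline and week 5 are the ones the objective is about, and they are flagged for correction before #3.

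The figure matters for planning the future trial. Medication changes in eligible patients who are not randomized are taken from the EHR, without study calls, to describe usual practice (sections 4.1 and 9.6.2). Accuracy measured after prompted correction does not describe those charts.

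The recommendation endpoint has a related weakness. Section 3.1 recognises that a patient given the guide may stop aspirin or start an over-the-counter PPI without asking a clinician. If that patient reports it at week 5 and the nurse updates the list, the wording of section 4.1 lets the update count, although no clinician recommended anything. This can happen only in patients who were reached, while chart review covers everyone.

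**Working it through.** The plan gives no discrepancy rate and no EHR-accuracy figure, so there is no figure of its own to reproduce. Two things can be checked: the order of events, and what one edited chart is worth.

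**Order of events**
1. Week 5: call, comparison with the list, message if they disagree (section 9.2.2).
2. The nurse may edit the chart. Nothing says how often.
3. Weeks 15-17: assessment #3, in completers of #1 only. The list is compared with self-report, and a further message may follow.
4. Chart review for exploratory outcomes continues to week 28 (section 1.3), after both messages.

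No section requires the list to be recorded as it stood before step 2. No section separates an edit that follows a study message from any other edit. Nurse involvement does not separate them either, because in the facilitation arm nurses also pend orders on a clinician's instruction (section 7.1.1).

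**What is already covered.** By eligibility, every list at entry shows an antiplatelet drug and no PPI (sections 6.2.1 and 6.3.1). The retrospective questions at week 5 therefore show baseline list errors among respondents, whatever is edited later.

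**Value of one chart**

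Inputs: 40 to 51 patients (section 6.1.1) and the 80% planning rate (section 11.1.1).
- Completers of #1: 0.80 × 40 = 32; 0.80 × 51 = 40.8, about 41.
- Accuracy for one drug = correct lists / n, so one list moved from wrong to right adds 1/n.
- If all completers also complete #3: 1/41 = 2.4 points; 1/32 = 3.1 points.
- If 70% do (an assumption, not in the plan): 0.70 × 32 = 22.4, about 22, and 0.70 × 41 = 28.7, about 29. Then 1/29 = 3.4 points and 1/22 = 4.5 points.
- Recommendation proportion, per edit wrongly scored: 1/51 = 2.0 points; 1/40 = 2.5 points.

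The accuracy values apply only to a chart that would still have been wrong at #3 without the prompt. A chart that usual care would have corrected in the interval adds nothing.

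**The case against.** Much of this may be handled in practice. The assistant has to look at the list to find a contradiction, so the uncorrected list is seen at the call. Chart review is scheduled before week 5 as well as after it. The unnamed time points in section 11.7.1 probably include week 5, since section 6.6.1 gives EHR accuracy as a purpose of that call. The natural reading of the #3 endpoint is the list as compared on that call, not after a later edit. The recommendation endpoint is limited to the patient's own clinicians, and a careful abstractor may discount a nurse's reconciliation. All of this is fair and keeps the point small. But these provisions allow a pre-reconciliation reading without requiring one, and the clinician limit reduces the risk of misscoring without removing it, because a list change alone is still accepted as the indicator.

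Stronger readings do not hold:
- A reader might infer that the #3 figure will be used to adjust or validate the usual-practice data. No section says so.
- A reader might infer a large bias, or one exceeding sampling error. That needs the number of wrong lists and the share that nurses correct, and the documents give neither.
- A reader might extend the point to the endpoint counting clinicians who appropriately documented changes in the list. That endpoint already requires the clinician to have done the documenting, so no added rule is needed.

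**Conclusion.** The point holds as a low-severity, cheap improvement. As written, the plan yields an EHR-accuracy figure at #3 for charts that have had a study-prompted chance of correction. To the extent nurses act, the figure is too favourable for charts without study calls. The plan also allows a prompted edit to be scored as a clinician recommendation.

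The size cannot be derived and is zero if no chart is edited. Per chart it is 2.4 to 3.1 points of one drug's accuracy, assuming 80% complete #1, all of those complete #3, and the chart would otherwise still have been wrong. Per misattributed edit it is 2.0 to 2.5 points of the recommendation proportion.

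Only exploratory, descriptive endpoints are affected. The primary endpoint, the secondary endpoint, the baseline-use endpoints and the interview-based medication-change endpoint are not.

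**What to change.** Keep the reconciliation message. Then:
1. Record the MiChart list as it stands before each call (#1 and #3). Name week 5, before reconciliation, as one of the time points in section 11.7.1, and report it beside the #3 result as the estimate of uncorrected accuracy.
2. Label the #3 result as following a study-prompted correction opportunity, and report how many messages were sent and how many charts were edited.
3. For the recommendation endpoint in section 4.1, do not count a list change that follows a study message unless a clinician note, message or order in the EHR supports it.

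The cost is a few sentences in the analysis section and a little extra abstraction for about 32 to 41 patients. Care, calls and data sources do not change. The downsides are a possibly less favourable accuracy figure and the possible loss of a few real recommendations that were never documented.
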